9.5 Point of randomisation

In person visit when the device is allocated.

9.6 Total expected duration of the clinical investigation.

12 weeks. Rolling recruitment over 5 month period, garment fabrication and fitting, 12 weeks home use, return of device. Total for study as a whole 9 months.

10 Study Procedures

10.1 Description of all the clinical investigation-related procedures that subjects undergo during the clinical investigation including any deviation from normal clinical practice.

A screening clinic visit will take place after an initial phone eligibility check to ensure that all participants have been diagnosed with knee OA according to the American College of Rheumatology criteria [13].

People who screen positive and consent to be part of the trial will be asked to attend three visits in person, complete follow-up questionnaires, and will receive a maximum of 4 phone calls over a period of approximately 3 months. The visits in person will take place in facilities within the University of Southampton, either at Winchester School of Art or Southampton General Hospital, on a mutually convenient date (daytime or exceptionally in the evenings).

In the first in person visit, a research nurse will take body measurements and will ask participants to try the standard size of TENS garment, which is closest to their measured size. After that, when the garment is ready, participants will visit the lab at Winchester School of Art to collect a garment with instructions and will receive guidance on what they need to do at home. They will be instructed to use the garment at least 5 out of the 7 days for 12 consecutive weeks. People will choose whether they prefer to undergo daily TENS in one session of 30 to 60 minutes or two separate sessions with a duration of 30 minutes each.. Participants will be given either an intervention or sham device – only the member of the research team distributing the garment at this point will be aware of which has been assigned.

We will collect information at baseline (on supply of wearable sleeve) and at 1, 4, 8 and 12-weeks follow-up of supply of the wearable device. Data collection will be using hard copies of questionnaires supplemented by phone calls at weeks 1, 4 and 8 as needed. Hard copies of all questionnaires will be provided at baseline together with a diary to record daily use. After 12 weeks we will schedule a final session in the lab in which participants will return the garment to the lab and provide their feedback.

10.2 Activities performed by sponsor representatives (excluding monitoring).

Not applicable.

10.3 Any known or foreseeable factors that can compromise the outcome of the clinical investigation or the interpretation of results.

None

10.4 The methods for addressing these factors in the clinical investigation, for example, by subject selection, clinical investigation design, such as stratified randomisation, or by statistical analysis shall be described.

Not applicable

10.5 The follow-up period during the clinical investigation shall permit the demonstration of clinical performance, effectiveness or safety over a period of time sufficient to represent a realistic test of the investigational device and allow any risks associated with adverse device effects to be identified and assessed.

The 12 week follow-up period during the clinical investigation shall permit the demonstration of clinical performance, effectiveness or safety over a period of time sufficient to represent a realistic test of the investigational device and allow any risks associated with adverse device effects to be identified and assessed.

Data on socio-demographic and clinical characteristics, pain, function, skin reaction, medication taken, use of assistive devices, and any adverse reaction will be collected as shown in Table 1. Medication use will be recorded at each time point, with indication. Adverse events will be recorded at each time point. Safety reporting will follow GCP guidance with suspected unexpected serious adverse events reported to the MHRA. An independent data monitoring committee will be established to provide overall governance of the trial. Monitoring of the trial will be undertaken by an independent commercial organisation to enable sponsorship by the University Hospital Southampton NHS Foundation Trust.

Table 1. Timeline for data collection process

·	Baseline	1-week Follow Up (FU)	4- week FU	8- week FU	12- week FU
Socio-demographic characteristics	х				
Clinical characteristics	х				
Analgesia to manage knee pain	х	х	Х	Х	Х
Visual Analog Scale	х	Х	Х	х	х
Adverse effects		х	х	х	х
Western Ontario and McMaster Universities Arthritis Index	х				х
Oxford Knee Score	х		х	х	х
EuroQol-5 Dimensions-5 Levels	х		Х	х	х
Modular Resource-Use Measure	х		х	х	х
Questions related to usability of the garment					Х

10.6 What specific medical care is appropriate to be provided for the subjects after the clinical investigation has been completed

Not applicable

10.7 Recommended follow-up for the subjects after the clinical investigation has been completed

Not applicable

10.8 Final disposition or potential future use of samples obtained from subjects, if applicable.

Not applicable

11 Monitoring plan

This study will be monitored by PHARMExcel and may be subject to monitoring and audit by University Hospital Southampton NHS Foundation Trust, under their remit as sponsor and other regulatory bodies to ensure adherence to ICH GCP, UK Policy Framework for Health and Social Care Research, applicable contracts/agreements and national regulations. All study related documents will be made available on request for monitoring and audit by UHS, the relevant REC or other licensing bodies. A CRO, PHARMExcel will monitor the clinical study.

12 Statistical Design and analysis

12.1 Analysis population (e.g. intention-to-treat, per-protocol, as-treated) and procedures that take into account all the data.

Analysis will be on the intention-to-treat population. Levels of missing data will be monitored and we will consider whether data are missing not at random. Multiple imputation methods will be considered if <10% of the primary outcome data are missing (at random).

12.2 Descriptive statistics of baseline data, treatments, safety data and where applicable, primary and secondary endpoints.

Descriptive statistics of baseline clinical data will be presented by treatment arm (ITT).

Clinical data analysis: Pain score, motor function, safety and quality of life data will be summarised and will be reported according to CONSORT: extension to pilot and feasibility trials guidelines.

Changes in clinical outcomes from baseline will be summarised within treatment (ITT)

Process and feasibility outcomes such as recruitment and retention rate will be presented with 95% confidence intervals; adverse events (safety data) will be presented by treatment arm.

12.3 Analytical procedures including measures of precision such as confidence intervals, if applicable.

Changes in clinical scores from baseline will be summarized within treatment arm with 95% confidence intervals.

The primary analysis will compare the primary outcome measures (knee pain) in mixed-effects linear regression models to account for repeated measures from baseline to 12-weeks follow-up, with treatment arm as a fixed effect along with other potential important baseline factors such as socio-demographic and clinical characteristics. Recruitment and retention rates will be summarized overall and presented with 95% confidence intervals.

12.4 The significance level and the power of primary endpoint(s) and the overall statistical testing strategy, if applicable.

A significance level of 5% and power of 80% will be used.

- 12.5 Sample size calculation and justification taking into account:
- 12.5.1 All relevant clinical data on outcome variable and effect size, if applicable

These will be explored in this study.

12.5.2 Assumptions of expected outcomes across treatment groups, if applicable.

Not applicable.

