6.7 Risk-to-benefit rationale

This is a low risk device and potential benefits outweigh risks by reducing pain and improving quality of life.

7 Objectives and hypotheses of the clinical investigation

7.1 The purpose of the clinical investigation, claims for clinical performance, effectiveness or safety of the investigational device that are to be verified.

Pain relief, reduction in stiffness, further highlight efficacy of the device for pain relief. No safety aspects will be verified.

7.2 Objectives, primary and secondary – superiority.

a) Primary objective

The main objective of the study is to assess the efficacy of the new wearable TENS device to reduce OA knee pain and further confirm the usability of the device at home over a longer period.

b) Secondary objectives

As secondary objectives the trial will evaluate:

- Changes in functional outcomes observed in the intervention group (TENS arm) and control group (Sham arm),
- Effect of using the knee wearable sleeve on health care utilization, and
- Usability of the prototype over a longer (12 week) period.
- 7.3 Scientific justification and clinical relevance for effect sizes, non-inferiority margins or equivalence limits, where applicable.

Not applicable.

7.4 Primary and secondary hypotheses, if applicable.

- The e-textile wearable TENS is able to reduce pain for people with knee OA.
- The device is suitable for home use in terms of user comfort, ease of use, and safety (e.g. no adverse events).
- The device may improve the functions measured via the Oxford Knee Score, Western Ontario and McMaster Universities Arthritis Index (WOMAC), EuroQol-5 Dimensions-5 Levels (ED-5Q – 5L), and Modular Resource Use Measure (ModRUM).

7.5 Risks and anticipated adverse device effects that are to be assessed.

Risk: Minor skin irritation. No adverse device effects anticipated.

8 Design of the trial investigation

8.1 Description of the design type of clinical investigation to be performed (e.g. randomised, blinded or open-label, parallel groups or crossover, multicentre, international) the control group, (e.g. comparative claim and reversible treatment of a chronic state) and the comparator with rationale and justification for the choice. Absence of control(s) shall be justified.

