This is a double-blind 2-arm parallel group randomised controlled trial of 80 people comparing the efficacy on knee pain relief in patients with medically-diagnosed knee osteoarthritis. 80 people will be randomly allocated in a 1:1 ratio to the intervention arm (an active TENS group) or to the sham (control) group who will have TENS programmed to switch off automatically after an initial 4 minutes of stimulation.

8.2 Description of the measures to be taken to minimize or avoid bias, such as randomisation, concealment of allocation, blinding/masking, and management of potential confounding factors.

Participants will be randomly allocated to treatment or control (sham treatment) in a 1:1 ratio according to a randomisation schedule held by the statistician. The schedule will be based on a block randomisation with varying block sizes to avoid imbalance in treatment allocation with respect to known and unknown confounders, and to avoid any potential for anticipation of future participants' treatment allocation.

8.3 Primary and secondary endpoints, with rationale for their selection and measurement. If applicable, composite endpoints, with rationale for their selection and measurement.

To evaluate efficacy of TENs on knee pain relief we will collect data on: knee pain recorded on a Visual Analog Scale, and WOMAC-pain sub-scale.

Secondary outcomes of the study include the Oxford Knee Score, Western Ontario and McMaster Universities Arthritis Index, EuroQol-5 Dimensions-5 Levels, Modular Resource Use Measure and a list of adverse reactions.

A detailed list of the outcome measures is included in the Investigator Brochure - document 3.

8.4 Methods and timing for assessing, recording, and analysing variables.

Clinical outcomes will be reported on paper questionnaires. We will collect baseline information prior to supply for the intervention/sham device. Follow up data will be collected at 1, 4, 8 and 12-weeks after supply of the wearable device. Phone calls to supplement data collection at weeks 1, 4 and 8 will be employed as appropriate.

Data from paper questionnaires will be doubled entered onto a database at the MRC LEC and then transferred to the statistician for analysis.

8.5 Equipment to be used for assessing the clinical investigation variables and arrangements for monitoring maintenance and calibration.

Not applicable.

8.6 Any procedures for the replacement of subjects.

Not applicable

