We will compare baseline characteristics as an assessment of the success of the randomisation. No formal statistical tests will be used to compare baseline characteristics between the randomised treatment groups.

12.10 Management of potential confounding factors (e.g. adjustment, stratification, or stratified randomisation).

Potential confounding factors such as baseline clinical characteristics will be adjusted for as fixed effects in mixed-effects linear regression models.

12.11 Description of procedures for multiplicity control and adjustment of error probabilities, if applicable.

Not applicable.

12.12 Specification of subgroups for analysis, if applicable, or if response to treatment is expected to be different in these groups.

Not applicable.

12.13 Management, justification, and documentation of missing, unused or spurious data, including drop-outs.

All efforts will be made to collect complete data. An assessment on the amount of missing data, especially in the primary outcome, will be made. We will consider whether data are missing not at random. Multiple imputation methods will be considered if <10% of the primary outcome data are missing (at random).

12.14 Exploratory analysis and sensitivity analysis (e.g. to explore robustness of results of primary and secondary analysis with respect to different methods used for handling missing data), if applicable.

Not applicable

12.15 Procedures for reporting any deviation(s) from the original statistical analysis plan.

These will be reported according to CONSORT guidelines.

12.16 For multicentre clinical investigations, a strategy for handling the potential imbalance of the numbers of subjects across investigation sites.

Not applicable

12.17 A strategy for pooling data, if applicable.

Not applicable.

13 Data Management

13.1 Methods (e.g. CRF) for data entry and collection.

The questionnaires will be completed in paper format. They will then be double data entered by Data Processing Assistants at the MRC LEC. Monitoring by PHARMExcel will occur throughout the study to ensure that issues and data queries are dealt with promptly, details will be contained in a study specific monitoring plan.

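### Section 12.3 states a between-arm model for knee pain only; for function and quality of life it states within-arm change, which cannot address the section 7.4 hypothesis

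*Protocol*

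**What the plan says.** **Aims.** Protocol section 7.2 labels the objectives as superiority. Its first secondary objective is to evaluate "Changes in functional outcomes observed in the intervention group (TENS arm) and control group (Sham arm"), which describes change in each group and does not name the difference between them. Section 7.4 adds the hypothesis: "The device may improve the functions measured via the Oxford Knee Score", and continues with WOMAC, EQ-5D-5L and the resource-use measure. Section 8.3 lists the same instruments: "Secondary outcomes of the study include the Oxford Knee Score, Western Ontario and McMaster Universities Arthritis Index", followed by the others.

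**Analyses.** Section 12.2 says: "Pain score, motor function, safety and quality of life data will be summarised and will be reported according to CONSORT: extension to pilot and feasibility". The same section has changes from baseline summarised within treatment. Section 12.3 repeats this with intervals: "Changes in clinical scores from baseline will be summarized within treatment arm with 95% confidence intervals". It then gives the between-arm analysis: "The primary analysis will compare the primary outcome measures (knee pain) in mixed-effects linear regression models", with treatment arm as a fixed effect.

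**General statements.** The summary table lists mixed-effects linear models as a method without naming an outcome. Section 12.10 does the same for covariate adjustment: "Potential confounding factors such as baseline clinical characteristics will be adjusted for as fixed effects in mixed-effects linear regression models".

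**The concern.** The hypothesis in 7.4 is causal: it concerns what the device does to function and quality of life. The change from baseline in the TENS arm is the sum of any device effect, the response to wearing a sham-like device, natural fluctuation and regression to the mean. In a blinded randomised trial the sham arm allows the last three to be subtracted, and the analysis stated for these scores does not carry out that subtraction.

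Regression to the mean is a live possibility because section 9.1 selects participants on pain (VAS 3 to 7), and function scores are likely to move with pain. The entry window is bounded on both sides, so the document does not settle the direction or size of this effect.

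At stake is how the secondary results will be read. Two within-arm intervals placed side by side invite the reader to note which one excludes zero, and that is not a comparison of the arms. The trial is also meant to inform a definitive trial, for which an estimated difference with its interval would be more useful than two separate changes.

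**Working it through.** **1. The plan's own figure.** Sections 12.4 and 12.5 give 5% significance, 80% power, a standardised effect of 0.69, and 35 complete cases per arm from 80 recruited. Sidedness is not stated; two-sided is assumed.
- Normal approximation: n per arm = 2(1.96 + 0.842)² / 0.69² = 33.
- Power at 35 per arm by noncentral t: 81.2%.
- Recruitment: 70 / (1 − 0.125) = 80.

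The figure reproduces. It is used below only to fix n = 35 per arm.

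**2. Which analysis attaches to which outcome.**

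| Outcome | Within-arm change with 95% CI | Between-arm model named |
|---|---|---|
| Knee pain (VAS, WOMAC pain) | Yes | Yes (12.3) |
| Oxford Knee Score | Yes | No |
| EQ-5D-5L | Yes | No |
| Non-pain WOMAC scores | Yes | No |

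WOMAC pain is placed in the first row because 8.3 lists it with the VAS as a knee-pain efficacy measure and 12.3 refers to the primary measures in the plural.

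**3. What a within-arm interval shows when the device does nothing.** Assumptions, none of them in the protocol: both arms improve by the same amount d (in SDs of the score), the SD is equal at baseline and week 12, and the baseline-to-week-12 correlation is ρ.
- SD of change = √(2(1 − ρ)).
- Standard error of the mean change = √(2(1 − ρ)/35).
- Noncentrality = d / standard error; critical value t(34) = 2.032.

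For d = 0.5 and ρ = 0.5: SD of change = 1.0, standard error = 0.169, noncentrality = 2.96, and the probability that the TENS-arm interval lies wholly on the side of improvement is 82%.

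| Shared change d | ρ = 0.3 | ρ = 0.5 | ρ = 0.7 |
|---|---|---|---|
| 0.3 SD | 31% | 41% | 60% |
| 0.5 SD | 68% | 82% | 96% |
| 0.7 SD | 93% | 98% | 99.9% |

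Under the same assumptions a between-arm 95% interval excludes zero 5% of the time, 2.5% in favour of TENS, whatever d and ρ are.

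**4. A milder misreading.** Suppose the reader looks at both arms and is misled only when TENS shows improvement and sham does not. With no device effect this has probability p(1 − p), where p is the entry in the table above. At d = 0.5 and ρ = 0.5 it is 0.82 × 0.18 = 15%. Over the grid it runs from under 0.1% (d = 0.7, ρ = 0.7) to 24% (d = 0.3, ρ = 0.5).

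**5. What a between-arm estimate would deliver.** With 35 per arm and no adjustment, the 95% half-width is 1.995 × √(2/35) = 0.48 SD. Adjusting for baseline multiplies this by about √(1 − ρ²). At ρ = 0.5 that gives 0.41 SD (0.46 SD at ρ = 0.3, 0.34 SD at ρ = 0.7). This is wide, but it estimates the quantity that 7.4 asks about.

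**The case against.** Several points on the other side stand.

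- **That within-arm change is the sole permitted analysis.** A reader might infer this, but no text says so. The within-arm sentence covers pain too, and pain also has a between-arm model, so the two evidently coexist. The summary table and 12.10 mention mixed models without limiting them to pain. However, neither commits to a between-arm estimate for any secondary score.
- **That the sham arm goes unused.** This is also tempting and not supported. Sham changes are summarised beside TENS changes, and sham is the comparator for pain.
- **That the plan would declare benefit when the TENS interval excludes zero.** No such rule exists. Section 12.7 sets no pass/fail criteria, the wording in 7.4 is tentative, and 12.2 follows the reporting guidance for pilot trials. The 82% therefore describes an assumed reading that ignores the sham column. Step 4 gives the lower figure for a reader who looks at both.
- **That secondary models belong in the SAP.** Often they do, and silence alone would be no finding. Here the protocol is not silent: it states a method for these scores, and that method cannot answer the hypothesis it sets for them.
- **That within-arm intervals suit a pilot.** They do help in describing variability, and there is no need to remove them. They still do not estimate a device effect.

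**Conclusion.** The point holds as a mismatch between aim and stated method. For Oxford Knee Score, EQ-5D-5L and the non-pain WOMAC scores, 12.2 and 12.3 state within-arm change and no active-minus-sham estimate, while 7.4 hypothesises improvement due to the device. The primary pain analysis and the sample size are unaffected.

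The possible size of the problem rests on assumed values of shared change and correlation, on 35 complete cases per arm and on two-sided 95% intervals. Under those assumptions, a TENS-arm interval showing improvement with no device effect has probability 82% in the central case and 31% to over 99% across the range. This measures how little such an interval says about the device; it is not an error rate of any rule in the protocol. The change is best regarded as a free improvement, since it costs almost nothing and uses data already planned.

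**What to change.** Add to section 12.3 a sentence to this effect: Oxford Knee Score, EQ-5D-5L and the non-pain WOMAC scores will each be reported as the active-minus-sham difference at week 12 with a 95% CI, adjusted for the baseline value of the same score, as estimation and not as a powered test.

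The schedule in Table 1 supports this. Oxford Knee Score and EQ-5D-5L are collected at baseline and weeks 4, 8 and 12, so a mixed model fits. WOMAC is collected at baseline and week 12, so ANCOVA fits.

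Keep the within-arm summaries as description, and state that they will not be used as evidence of a device effect.

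Cost: one or two sentences of wording. Visits, questionnaires and sample size do not change, and the models are of the kind already planned for pain.

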12.5.3 Adjustments due to any pre-planned interim analyses, if applicable

Not applicable. There will be no interim analyses.

12.5.4 Detectable effect size and non-inferiority margin, which shall be smaller than the detectable effect size and justified with reference to the effect of the comparator, if applicable;

Non-inferiority margin is not applicable. Detectable effect size is a standardized effect size of 0.69.

12.5.5 Randomisation allocation ratio

Ratio = 1:1

12.5.6 Expected drop-out rate, such as withdrawal, lost to follow-up, death (unless death is an endpoint).

80 participants will be recruited into the study, 40 to each treatment arm. We will recruit 80 participants (40 per trial arm) to achieve a sample size of N=70, 35 in each treatment arm, allowing a 12.5% drop-out rate. We anticipate that our drop -out rate will be lower than our original, conservative, estimate of 25%. However,

if we do not achieve a sample of N=70 (35 in each treatment arm) complete data by recruiting 80 participants, we will continue to recruit until we have achieved our planned N=70 participants with complete data.

12.5.7 All the statistical parameters and methods used to calculate sample size or the non-inferiority margin shall be clearly provided.

We will assess the efficacy of the new TENS wearable device to reduce OA knee pain. A sample size of complete data of N=70 (35 in each treatment arm) will allow us to detect a standardized effect size of 0.69, with 5% significance level and 80% power.

Additionally, our sample size calculation has been calculated assuming this is a pilot randomised controlled trial that will gather data to inform a future definitive trial. Teare et al [15] conducted an extensive simulation study considering the precision gained per additional 5 patients in the estimation of the variability of a continuous normally distributed outcome. Their work demonstrated that a total sample size of 70 is required to estimate the variability of a continuous outcome to have adequate data to inform the sample size for a fully powered definitive RCT, with a sample size above 70 yielding little additional precision. Thus, this sample size will allow us to estimate the variability of the primary outcome to inform a future definitive RCT.

12.6 Rationale for the number of procedures to be performed by a single user as part of the learning curve and how these data are to be analysed, if applicable.

Not applicable.

12.7 Pass/fail criteria to be applied to the results of the clinical investigation.

Not applicable

12.8 The provision for an interim analysis, criteria for the termination of the clinical investigation on statistical grounds, where applicable.

Not applicable

12.9 Management of bias and, when randomisation, matching, or blinding are applied, plan for assessment of success thereof.

We will compare baseline characteristics as an assessment of the success of the randomisation. No formal statistical tests will be used to compare baseline characteristics between the randomised treatment groups.

12.10 Management of potential confounding factors (e.g. adjustment, stratification, or stratified randomisation).

Potential confounding factors such as baseline clinical characteristics will be adjusted for as fixed effects in mixed-effects linear regression models.

12.11 Description of procedures for multiplicity control and adjustment of error probabilities, if applicable.

Not applicable.

12.12 Specification of subgroups for analysis, if applicable, or if response to treatment is expected to be different in these groups.

Not applicable.

12.13 Management, justification, and documentation of missing, unused or spurious data, including drop-outs.

All efforts will be made to collect complete data. An assessment on the amount of missing data, especially in the primary outcome, will be made. We will consider whether data are missing not at random. Multiple imputation methods will be considered if <10% of the primary outcome data are missing (at random).

12.14 Exploratory analysis and sensitivity analysis (e.g. to explore robustness of results of primary and secondary analysis with respect to different methods used for handling missing data), if applicable.

Not applicable

12.15 Procedures for reporting any deviation(s) from the original statistical analysis plan.

These will be reported according to CONSORT guidelines.

12.16 For multicentre clinical investigations, a strategy for handling the potential imbalance of the numbers of subjects across investigation sites.

Not applicable

12.17 A strategy for pooling data, if applicable.

Not applicable.

13 Data Management

13.1 Methods (e.g. CRF) for data entry and collection.

The questionnaires will be completed in paper format. They will then be double data entered by Data Processing Assistants at the MRC LEC. Monitoring by PHARMExcel will occur throughout the study to ensure that issues and data queries are dealt with promptly, details will be contained in a study specific monitoring plan.

13.2 Procedures used for CRF tracking, data review, database cleaning, and issuing and resolving data queries. Specifically, timely, and reliable processes for recording data and rectifying errors and omissions, medical coding uniformity, and reconciliation, if applicable, are necessary to ensure delivery of a quality database and the achievement of the clinical investigation objectives through the implementation of the planned analysis.

As above.

13.3 Procedures for verification, validation, and securing of electronic clinical data systems, if applicable.

Not applicable.

13.4 Procedures to maintain and protect subject privacy.

All investigators and study staff will comply with the Data Protection Act 2018 requirements for the collection, storage, processing and disclosure of personal information and will uphold the Act's principles. Study documents (paper and electronic) will be collected and retained in accordance with the Data Protection Act 2018 in a secure location during and after the study has finished.

13.5 Methods for database locking at the start of the analysis and storage upon completion of the clinical investigation.

All data collected will be stored on a University computer protected by a password. Only researchers involved in data collection and the statistician in charge of analysing the data will be able to access this information.

Personal details (i.e., name, surname, e-mail address and phone number) will be kept under a protected password document on a secure server and separately from the rest of the data collected during the trial. Each participant will have a unique identification number that will ensure that the information is anonymous.

13.6 Procedures for data retention.

Data retention will be in line with University Hospital Southampton NHS Foundation Trust and the University of Southampton procedures.

13.7 Specified retention period.

All study documents will be archived securely for a minimum of 15 years in line with the Sponsor's policy.

